3.5 SAMPLE SIZE CONSIDERATIONS

The primary efficacy endpoint is the rate of subjects meeting the ACR20. This response rate will be compared in subjects who received a given dose of ABX464 or placebo by likelihood ratio chi-square test. The result of the test will be interpreted in a descriptive manner therefore no adjustment for multiple comparison is applied.

For the sample size assessment, the following assumptions will be made:

- Response rate (ABX464): 0.65
- Response rate (placebo): 0.25

According to literature the ACR20 response rate for ABX464 + MTX treated subjects is expected to be between 50% and 65% while that in the placebo + MTX group is assumed to be approximately 25 to 30% (Xeljanz® Summary of Product Characteristics; ORAL Standard Investigators - N Engl J Med 2012; 367:508-519 August 9, 2012).

- Type I error: 10% two-sided
- Group allocation rate (ABX464 / placebo): 1:1:1

If the above assumptions and definitions hold true with a sample size of 60 subjects receiving two doses of ABX464 or placebo in a ratio of 1:1:1 the study has 84% power to show a difference in response rate between one active study group and placebo.

Subjects who terminates the study prematurely will be considered failures therefore no adjustment for drop-outs is needed.

Primary safety endpoint is the rate of all treatment emergent adverse experiences. The above sample size is sufficient to detect an increase in general treatment emergent adverse experience rate from 10% to 50% with 89% power by likelihood ratio chi-square test on a 10%, two-sided significance level.

If approximately 20 subjects receive ABX464 the study has 88% chance to detect at least 1 specific treatment emergent AE if the underlying rate of occurrence is 1:10. When the underlying rate of occurrence is around 1:20 the sample size of 40 subjects receiving active treatment is sufficient to observe at least 1 such an event with a probability of 87% in the active treatment group.

3.6 RANDOMISATION

Eligible patients (i.e. those who fulfil all inclusion/exclusion criteria) will be randomized according to a 1:1:1 ratio into ABX464 100mg, ABX464 50mg or placebo treatment arms.

Up to 60 patients will be randomized in this study. At the beginning, the first 6 patients will be randomized to receive either ABX464 50mg (n=4) or its matching placebo (n=2). The Data Safety Monitoring Board (DSMB) will review the safety of these first 6 patients dosed for at least 2 weeks. Once the DSMB recommendation is granted, the next patients will be randomized to receive either ABX464 50mg, ABX464 100mg or placebo. Then, a second DSMB meeting will be held after the next 6 patients are randomized to check the tolerability of the 100mg dose. Once the DSMB recommendation is granted, the next patients will be randomized to receive either ABX464 50mg, ABX464 100mg or placebo.

Randomization will be performed via a centralized treatment allocation system that will be available 24 hours-a-day, 7 days-a-week. Randomization will be stratified according to previous exposure to anti-TNF α therapy. The bottle numbers to be used for a specific patient will be assigned according to a pre-defined randomization list.

4 STUDY VARIABLES AND COVARIATES

4.1 PRIMARY VARIABLE

The primary variable for statistical comparison between treatment groups will be the incidence of treatment-emergent adverse events in the ABX464 treated Patients versus placebo, categorized by severity.

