2.3. Primary Endpoint

The primary endpoint is the incidence of treatment-emergent adverse events in the ABX464 treated Patients versus placebo, categorized by severity.

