8.4. Safety Analyses

Adverse events will be coded using the standard dictionary (MedDRA) down to the lower level term (LLT).

An overall summary table will be presented (Any adverse event, any treatment emergent adverse event (TEAE), any serious adverse event (SAE), death, any grade 3 or higher adverse events from baseline to the end of Study. This analysis will be conducted on SAF population.

Two periods will be defined for TEAE:

- Any adverse event which occurs or worsens from first dosing to Day 84;
- Any adverse event which occurs after Day 84.

Adverse events will be described by primary system organ class and preferred term. Numbers and percentage of patients, and number of occurrences of adverse event will be presented for:

- TEAE;
- Serious TEAE;
- TEAE leading to drug discontinuation;
- TEAE of grade 3 or 4;
- TEAE for which relationship with the study drug is recorded as possible or probable.

Analysis of safety will be performed on the safety data set consisting all subjects who received at least one dose of ABX464 in the study.

Primary safety endpoint, the rate of all treatment emergent adverse experiences, will be compared in subjects who received a given dose of ABX464 or placebo by likelihood ratio chi-square test on a 10% two-sided significance level.

Further assessment of safety will be based on the frequency of adverse events (with and without regard to causality) graded according to the CTC-AE Classification and also, the review of individual values for clinical laboratory data, vital signs and ECG focusing on the detection of abnormal values and PCSAs [potentially clinically significant abnormalities (PCSAs) determined upon investigator considerations].

Adverse events will be tabulated (counts and percentages) by group. All adverse events will be listed, and the data will be tabulated by body system/organ class. Adverse event tabulations will include all treatment emergent adverse events, which will be further classified by severity, and relationship to treatment and dose level.

Clinical laboratory parameters, vital signs, ECG will be summarized by using descriptive statistics (n, mean, SD, SEM, median, minimum and maximum). Number of patients with at least one abnormal value will be tabulated (counts and percentages) for each parameter in summary shift tables, by group and dose.

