4.2.2 Other secondary endpoints

- Change from Baseline in the following disease parameters at Week 2, Week 4, Week 8 and Week 12:
 - Individual components of the ACR20 response (CRP, TJC(28), SJC(28), Pain-VAS, PtGA, PrGA, HAQ-DI)
 - Erythrocyte Sedimentation Rate (ESR);
 - DAS28-CRP and DAS28-ESR. The components of DAS28 assessment include TJC(28), SJC(28), CRP/ESR, and PtGA;
 - SDAI score which includes TJC(28), SJC(28), CRP, PtGA, and PrGA;
 - CDAI score which includes TJC(28), SJC(28), PtGA, and PrGA;
 - Functional Assessment of Chronic Illness Therapy (FACIT)-Fatigue score
- Proportion of patients achieving at Week 2, Week 4, Week 8 and Week 12:
 - ACR20/50/70 response
 - Categorical DAS28-CRP response. Proportion of patients achieving categorical DAS28-CRP response will be measured as moderate/good European League Against Rheumatism (EULAR) response at each assessment time point;
 - Low Disease Activity (LDA) ($DAS28 \leq 3.2$)
 - DAS28-ESR remission ($DAS28 < 2.6$)
 - ACR/EULAR remission (TJC(28), SJC(28), CRP, and PtGA: all ≤ 1);
 - SDAI remission ($SDAI \leq 3.3$);
 - CDAI remission ($CDAI \leq 2.8$).
- Concentration of miR-124 expression in total blood (determined by qPCR) at baseline and week 8
- Change from Baseline in miR-124 expression in total blood at Week 8
- PK parameters:
 - Pre-dose plasma concentration of ABX464/N-Glu at Week 2 and Week 8;
 - Post-dose plasma concentration of ABX464/N-Glu at 1-, 2- and 3-hours post-dose at Baseline, Week 2 and Week 8;
 - Trough plasma concentration of ABX464/N-Glu at End of Study Visit
- The number of incidences of treatment-emergent serious adverse events;
- The number of incidences of treatment-emergent adverse events of special interest;
- The number of incidences of adverse events leading to investigational product discontinuation;
- The number of incidences of clinically significant laboratory abnormalities;
- The number of incidences of all AE (causally related and non-related) and SAE, further categorized by severity.

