11.6 SAFETY ANALYSES

11.6.1 Adverse Events

An overall summary table will be presented (any adverse event, any treatment emergent adverse event (TEAE), any serious adverse event (SAE), death, any grade 3 or higher adverse events from baseline to the end of Study) (*Table 14.3.1.1*). This analysis will be conducted on SAF population.

Primary safety endpoint, the rate of all treatment emergent adverse experiences, will be compared in subjects who received a given dose of ABX464 or placebo by likelihood ratio chi-square test on a 10% two-sided significance level (*14.3.1.2.1*).

Two periods will be defined for TEAE:

- Period I: any adverse event which occurs or worsens from first dosing to Day 84;
- Period II: any adverse event which occurs after Day 84.

Adverse events will be described by primary system organ class and preferred term according to the two periods. Numbers and percentage of patients, and number of occurrences of adverse event will be presented for:

- TEAE (Table 14.3.1.2.2 and Table Table 14.3.1.2.3);
- Serious TEAE (Table 14.3.1.3.1 and Table Table 14.3.1.3.2);
- TEAE leading to drug discontinuation (Table 14.3.1.4.1 and Table Table 14.3.1.4.2);
- TEAE of grade 3 or 4 (Table 14.3.1.5.1 and Table Table 14.3.1.5.2);

Further assessment of safety will be based on the frequency of adverse events (with and without regard to causality) graded according to the CTC-AE Classification and also, the review of individual values for clinical laboratory data, vital signs and ECG focusing on the detection of abnormal values and PCSAs [potentially clinically significant abnormalities (PCSAs) determined upon investigator considerations].

Adverse events will be tabulated (counts and percentages) by group. All adverse events will be listed, and the data will be tabulated by body system/organ class. Adverse event tabulations will include all treatment emergent adverse events, which will be further classified by severity, and relationship to treatment and dose level.

All adverse events (AE) will be classified using the version of the MedDRA coding dictionary specified in the DHM.

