Events will be classified as treatment-emergent if they started or increased in severity on or after the first date and time of medication dosing at Visit 1 and up to study closure or withdrawal date. If an event start date is partial, then the start day, month, year or stop date will be used to determine if the event is treatment-emergent. If the classification of the AE cannot be determined from the data available, then the event will be considered treatment-emergent.

Treatment-emergent adverse events (TEAEs) will be further classified as follows:

Severe TEAEs: Severity classified as 'severe' (Common Toxicity Criteria [CTC] grade 3 or 4) or missing.

Serious TEAEs: Serious classified as 'yes' or missing.

Drug-related TEAEs: Relationship to study drug classified as 'related' or missing.

Serious drug-related TEAEs: Both serious and drug-related, as specified above.

TEAEs leading to withdrawal from study: Action taken classified as 'discontinued'.

All AE summary tables will show the number (%) of patients having at least one event and the number of events in each treatment group and overall. Median duration of AEs (from baseline to occurrence) will be presented in the tables. Note: If a patient has multiple AEs with the same preferred term, these will be summarised once within the count for N (%) of patients, but each event will be counted within the number of reports n of each AE. Changes in severity of the same AE (if collected) will be counted only once within the number of reports n of each AE.

The following will be presented in listing format within the data summaries:

- Deaths (Table 14.3.2.1);

- Serious Adverse Events (*Table 14.3.2.2*);
- Adverse Events which Led to Withdrawal (*Table 14.3.2.3*).

All adverse events (including non-treatment-emergent events) recorded on the CRF will be listed within the data listings.

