14 LIST OF TABLES, FIGURES AND LISTINGS

14.1 LIST OF TABLES

Demographic Data

Table 14.1.1	Screening Failures	All Enrolled Patients
Table 14.1.2	Patient Disposition	All Randomised Patients
Table 14.1.3	Study Termination and Primary Reason for Withdrawal	All Randomised Patients
Table 14.1.4	Demographic and Baseline Characteristics	Full Analysis Set
Table 14.1.5.1	Medical History	Full Analysis Set
Table 14.1.5.2	Current Medical Conditions	Full Analysis Set

Efficacy Data

Table 14.2.1.1	Analysis of ACR20 Response Rate	Efficacy Set 1
Table 14.2.1.2	Analysis of ACR20 Response Rate	Efficacy Set 2
Table 14.2.1.3	Analysis of ACR20 Response Rate	PP Set
Table 14.2.2.1	Summary of Categorical ACR20 Response at Week 12	Efficacy Set 1
Table 14.2.2.2	Summary of Categorical ACR20 Response at Week 12	Efficacy Set 2
Table 14.2.3.1	Analysis of the individual components of the ACR20 response	Efficacy Set 1
Table 14.2.3.2	Analysis of the individual components of the ACR20 response	Efficacy Set 2
Table 14.2.4.1.1	Analysis of ESR	Efficacy Set 1
Table 14.2.4.1.2	Analysis of ESR	Efficacy Set 2
Table 14.2.4.2.1	Analysis of DAS28-CRP	Efficacy Set 1
Table 14.2.4.2.2	Analysis of DAS28-CRP	Efficacy Set 2
Table 14.2.4.3.1	Analysis of DAS28-ESR	Efficacy Set 1
Table 14.2.4.3.2	Analysis of DAS28-ESR	Efficacy Set 2
Table 14.2.4.4.1	Analysis of SDAI Score	Efficacy Set 1
Table 14.2.4.4.2	Analysis of SDAI Score	Efficacy Set 2
Table 14.2.4.5.1	Analysis of CDAI Score	Efficacy Set 1

Table 14.2.4.5.2	Analysis of CDAI Score	Efficacy Set 2
Table 14.2.4.6.1	Summary of FACIT-Fatigue Score	Efficacy Set 1
Table 14.2.4.6.2	Summary of FACIT-Fatigue Score	Efficacy Set 2
Table 14.2.5.1	Summary of Patients Different Responses and Remissions	Efficacy Set 1
Table 14.2.5.2	Summary of Patients Different Responses and Remissions	Efficacy Set 2

Safety Data

Table 14.3.1.1	Summary of Adverse Events	Safety Set
Table 14.3.1.2.1	Analysis of all Treatment-Emergent Adverse Events	Safety Set
Table 14.3.1.2.2	Treatment-Emergent Adverse Events, by SOC and PT: Period 1	Safety Set
Table 14.3.1.2.3	Treatment-Emergent Adverse Events, by SOC and PT: Period 2	Safety Set
Table 14.3.1.3.1	Serious Treatment-Emergent Adverse Events, by SOC and PT: Period 1	Safety Set
Table 14.3.1.3.2	Serious Treatment-Emergent Adverse Events, by SOC and PT: Period 2	Safety Set
Table 14.3.1.4.1	Treatment-Emergent Adverse Events Leading to Study Drug Discontinuation, by SOC and PT: Period 1	Safety Set

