Table 14.3.1.4.2	Treatment-Emergent Adverse Events Leading to Study Drug Discontinuation, by SOC and PT: Period 2	Safety Set
Table 14.3.1.5.1	Treatment-Emergent Adverse Events of Grade 3 or 4 by SOC and PT: Period 1	Safety Set
Table 14.3.1.5.2	Treatment-Emergent Adverse Events of Grade 3 or 4 by SOC and PT: Period 2	Safety Set
Table 14.3.2.1	Listing of Deaths	Safety Set
Table 14.3.2.2	Listing of Serious Adverse Events	Safety Set
Table 14.3.2.3	Listing of Withdrawals Due to Adverse Events	Safety Set
Table 14.3.3.1	Summary of Laboratory Parameters: Haematology	Safety Set
Table 14.3.3.2	Summary of Laboratory Parameters: Biochemistry	Safety Set
Table 14.3.3.3	Listing of Abnormal Laboratory Values	Safety Set
Table 14.3.4	Vital Signs	Safety Set
Table 14.3.5	Shift Table of Physical Examination	Safety Set
Table 14.3.6	Electrocardiogram	Safety Set
Table 14.3.7	Study Drug Exposure and Compliance	Full Analysis Set

Table 14.3.8	Prior Medications	Full Analysis Set
Table 14.3.9.1	Concomitant Medications	Full Analysis Set
Table 14.3.9.2	Changes in Concomitant Medications	Full Analysis Set

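### The primary safety variable is TEAE incidence by severity, but the plan compares only any TEAE yes/no, lists no TEAE table by grade, and its severe-TEAE category stops at grade 4

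*SAP*

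**What the plan says.** SAP 4.1 gives the primary variable for comparison between treatment groups as "the incidence of treatment-emergent adverse events in the ABX464 treated Patients versus placebo, categorized by severity". Protocol 2.3 says the same, and SAP 10.3 repeats the severity qualifier.

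Where the plan turns to analysis, severity disappears. SAP 3.5 and 11.6.1, and protocol 8.4 and 8.6, treat the primary safety endpoint as the rate of all TEAEs, compared by likelihood ratio chi-square at a two-sided 10% level. The table is 14.3.1.2.1, "Analysis of all Treatment-Emergent Adverse Events". Its shell has rows for N, Yes and No, and one p-value.

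Severity appears in four other places:

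- SAP 11.6.1 says in general terms that TEAE tabulations will be further classified by severity and by relationship to treatment. No table is cited for this.
- SAP 11.6.1 defines severe TEAEs as "Common Toxicity Criteria [CTC] grade 3 or 4) or missing".
- The only severity-restricted TEAE tables are 14.3.1.5.1, "Treatment-Emergent Adverse Events of Grade 3 or 4 by SOC and PT: Period 1", and its Period 2 counterpart.
- The overall summary, Table 14.3.1.1, covers "any grade 3 or higher adverse events from baseline to the end of Study". Its row counts all adverse events, not TEAEs alone.

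Two further outputs have no table in SAP 14.1. One is the secondary endpoint "The number of incidences of treatment-emergent adverse events of special interest". The other is the tabulation that protocol 8.4 asks for: "TEAE for which relationship with the study drug is recorded as possible or probable".

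**The concern.** The primary objective is safety, and two doses are compared with placebo. The endpoint says that severity matters, yet the only comparison collapses every patient to any event or none. If most patients in every arm have at least one mild event, a dose that turns mild events into moderate or severe ones leaves that comparison unchanged, and no listed table would show the shift across grades.

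The severe category adds a smaller fault. As written, a TEAE with a missing grade counts as severe and a grade 5 TEAE does not. Two tables in one report would then use different upper limits for high-grade events.

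**Working it through.** **1. The plan's own figure.** SAP 3.5 gives 60 patients at 1:1:1 (20 per arm), TEAE rates of 10% and 50%, a two-sided 10% level and 89% power. With the pooled normal approximation and mean rate 0.30:

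power = Φ{[|p2 − p1| − z√(2·p̄(1 − p̄)/n)] / √[(p1(1 − p1) + p2(1 − p2))/n]}

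= Φ{[0.40 − 1.645 × √(2 × 0.30 × 0.70/20)] / √[(0.09 + 0.25)/20]}

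= Φ{[0.40 − 1.645 × 0.1449] / 0.1304} = Φ(1.24) = 0.8925.

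The likelihood ratio non-central chi-square gives 0.8865, and exact enumeration of the likelihood ratio test gives 0.9125. The 89% reproduces, but it describes the yes/no comparison. The documents give no grade-specific rates, so no power for a comparison by severity can be taken from them.

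**2. What the yes/no test cannot see.** For a 2×2 table, G = 2 Σ O ln(O/E), referred to chi-square on 1 df.

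- Any TEAE in 10/20 and 10/20: every observed count equals its expected count, so G = 0 and p = 1.00.
- Grade 3 or higher in 6/20 and 0/20 among those same patients: the expected counts are 3 events and 17 non-events per arm. G = 2[6 ln(6/3) + 14 ln(14/17) + 20 ln(20/17)] = 2[4.159 − 2.718 + 3.250] = 9.38, p = 0.002.

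The first result is the one that Table 14.3.1.2.1 would print. The counts are hypothetical.

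**3. Where a grade 5 TEAE is and is not counted.**

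- Not counted: the severe-TEAE category of SAP 11.6.1; Tables 14.3.1.5.1 and 14.3.1.5.2 by SOC and PT.
- Counted by arm: the death row and the grade 3 or higher row of Table 14.3.1.1; any TEAE in Table 14.3.1.2.1; the serious-TEAE tables 14.3.1.3.1 and 14.3.1.3.2, because death is a seriousness criterion in protocol 7.2.
- Listed: Table 14.3.2.1 (deaths) and Listing 16.2.7, which carries the grade of each event.

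**4. How much an ordered comparison could add.** Score each patient's maximum grade and compare mean scores: Q = (difference in mean scores)² / [V(1/20 + 1/20)], where V is the pooled variance of the scores with divisor N − 1, referred to chi-square on 1 df at 10%. Power was simulated with grades 0 to 4 and 20 patients per arm.

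| Assumed rates | Yes/no test | Ordered test |
|---|---|---|
| Any TEAE 70% in both arms; grade 2+ 30% v 50%; same mix within grade 2+ in both arms | 11–12% | 20–22% |
| Same rates; mix within grade 2+ also worse on active | 11–12% | up to about 32% |
| Any TEAE 10% v 50% (the plan's rates) | 91% | about 87% |

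In the first two rows the yes/no test rejects at roughly its own false-positive rate. The grade mixes are assumptions, so the ordered-test figures are a range and not an estimate.

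**The case against.** The strongest defence is that the plan is consistent about what is tested: protocol 8.4 and 8.6 and SAP 3.5 and 11.6.1 all name the rate of all TEAEs. A fair reading is a binary test with a descriptive severity breakdown beside it. SAP 11.6.1 commits to that breakdown and Listing 16.2.7 holds the data. On this view a shell is missing, not an analysis. Much of this stands. It means that the gap can be closed without any new test. It does not remove the gap: SAP 4.1 still names the severity-categorised incidence as the variable for comparison, and a per-event listing is not an incidence by arm.

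A reader might infer that fatal events vanish from the report, so that one death in an arm of 20 would be a lost 5 percentage points. The documents do not support that. Step 3 shows them counted by arm in four places and listed in two more. The fault is confined to the severe label and its SOC/PT tables. The documents also do not define grade 5. Equating it with death relies on the CTC-AE scale they name, and protocol 7.2 and 7.5 record death as an outcome.

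A reader might also infer that the SAP introduced the narrower severity band. It did not: protocol 8.4 itself uses grade 3 or 4 in its TEAE list and grade 3 or higher in its overall summary. Correcting only the SAP would leave the two documents in conflict.

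Finally, nothing in the documents requires an ordered-grade test. SAP 10.6 says that test results are interpreted descriptively, and at the plan's own rates the ordered test is slightly weaker than the yes/no test.

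**Conclusion.** The point holds in this form. The primary variable includes severity, the only planned comparison does not, and no listed table shows TEAEs across grades. The severe-TEAE rule is wrong as written, because it admits a missing grade and leaves out grade 5.

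The yes/no test is blind to grade by construction: p = 1.00 and p = 0.002 can come from the same 40 patients. How much an ordered comparison would gain is uncertain. With any TEAE at 70% in both arms and grade 2+ at 30% versus 50%, it rejects in about 20–32% of trials, against 11–12% for the yes/no test, depending on assumed grade mixes that the documents neither give nor contradict. That supports reporting the grades. It does not support calling the any-TEAE test inadequate or replacing it.

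The missing tables for related TEAEs and for adverse events of special interest are secondary. They are output gaps and do not bear on the primary variable.

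**What to change.** 1. Extend Table 14.3.1.2.1 to show, per arm, the number and percentage of patients by maximum CTC-AE grade (none, 1, 2, 3, 4, 5) over all TEAEs. Align SAP 4.1 with 11.6.1: state that the any-TEAE rate is tested and that the distribution by maximum grade is descriptive, or name the comparison if one is intended.
2. Replace grade 3 or 4 with grade 3 or higher in the severe-TEAE definition of SAP 11.6.1, in Tables 14.3.1.5.1 and 14.3.1.5.2, and in the TEAE list of protocol 8.4.
3. Optional: a row-mean-score comparison of each dose with placebo on the ordered grades, labelled descriptive and placed beside the any-TEAE test. This adds one p-value per dose.
4. Secondary: add a table for adverse events of special interest (headache and skin lesions, protocol 5.3.2) and one for related TEAEs. For the latter, first reconcile the causality terms. Protocol 8.4 refers to possible or probable, protocol 7.5 records yes or no, protocol 7.6 sets out a five-level scale, and SAP 11.6.1 uses related or missing.

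The cost is SAP wording, a one-line protocol correction and a few shells. All the data are already in Listing 16.2.7. SAP 1.1 places finalisation before unblinding and database lock, so the change can be made without knowledge of results.
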